STUDY TITLE: Oral Penicillin Challenge in the Pediatric Emergency Department

NCT number: NCT03404804

Document date: 1aug22 last continuing review approval

PRINCIPAL INVESTIGATOR: [name], DO, MS

STUDY TITLE: Oral Penicillin Challenge in the Pediatric Emergency Department

A. PURPOSE OF THE STUDY

The purpose of this study is to utilize a parent-reported penicillin allergy questionnaire in a pediatric emergency department (PED) and demonstrate that providers will administer, and families will be willing to receive an oral penicillin challenge in those children deemed to have non-allergic and low-risk symptoms of true penicillin allergy.

B. HYPOTHESES / SPECIFIC AIMS

Aim 1: Demonstrate that a low-risk group of children with reported penicillin allergy will complete an oral penicillin challenge during a pediatric emergency department visit.

Hypothesis 1a: Providers will administer an oral penicillin challenge in the PED to children identified as having non-allergic and low-risk allergy symptoms.

Hypothesis 1b: Children with non-allergic and low-risk allergy symptoms will complete an oral penicillin challenge in the PED.

Aim 2: Conduct follow-up one day after oral challenge for all children and seven days after oral challenge for patients discharged with a prescription antibiotic to determine if a delayed or T-Cell mediated reaction occurs after exposure to multiple doses of penicillin or any other antibiotic prescribed at discharge.

Hypothesis 2a: Next day contact will be possible for over 95% of children who complete an oral challenge to demonstrate the ability to evaluate symptoms after PED discharge.

Hypothesis 2b: Seven-day follow-up will be completed in at least 90% of children who are discharged on a penicillin or other antibiotic to demonstrate the ability to monitor for delayed or T-Cell mediated reaction following the administration of multiple doses of penicillin.

Aim 3: Examine health care outcomes and prescription-related costs associated with illness treatment plans in children who are de-labeled as penicillin allergic after an oral challenge.

Hypothesis 3a: Health care outcomes (allergic reactions, number of illnesses, antibiotics prescribed, and ER/Urgent Care/Primary care visits) will be similar between children de-labeled as penicillin allergic compared to the general population.

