We have determined that we need 100 low-risk patients to complete the oral challenge at each of the three sites participating including here at Children's Hospital of Wisconsin. We will consent for questionnaire-screening approximately 500 children to achieve that number. This number is based off of our previous study; during that study 50 patients were approached per month for survey participation, 80% (40) agreed to participation, and 25% (10) of patients were found to have high-risk symptoms of allergy and thus were found to be ineligible. If 50% of patients with low-risk symptoms will have either provider/family refusal to oral challenge this will leave approximately 15 patients per month to complete an oral challenge and complete this portion of the study in approximately 7 months.

F. DRUGS OR PROCEDURES

Patient's family or guardian will be asked to answer an allergy symptom questionnaire that will be administered via an iPad. Patient's charts who are between the ages of 2-16 whose family has indicated an interest in allergy oral challenge will be reviewed.

If a child is eligible as defined in the questionnaire for allergy oral challenge and the family completes the challenge, then a gift card in the amount of \$50 will be provided for their time.

If a family completes all the telephone follow-up questionnaires at 6 and 12 months they will be mailed a \$25 gift card at the conclusion of each of the follow-up calls. (total of \$50 in follow-up stipends for full participation over one year.)

The allergy challenge consists of an oral amoxicillin challenge in the PED. A nurse will administer the oral challenge and will also be present during the process all of which will occur in the PED.

A follow up telephone survey monitoring for any adverse side effects/allergic reactions will be completed within 24 hours of the allergy oral challenge. If a patient receives a prescription for a penicillin or any other antibiotic then a follow up call will be made to monitor for any adverse side effects/allergic reactions at 7 days as well. Patients will also receive discharge instructions relevant to the study with phone numbers to call with questions.

A follow-up 5-minute phone survey will be completed by research staff to families of groups after their initial PED visit at 6 and 12 months. PI will review these results monthly or as relevant (notified by the study team) to monitor the long-term outcomes and safety of the protocol.

G. RISK CATEGORY:

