3) Research staff is present in the PED 16 hours per day on weekdays and 10 hours per day on weekends allowing for more than sufficient coverage to meet enrollment goals. We will limit administration of the oral challenge to 3 patients per day in an attempt to limit PED flow disruption. Administration of the questionnaire alone should not be disruptive to flow.

The appropriately trained research personnel will be identified in the registration page of this submission.

O. Statistical Analysis plan

Data collection and Management:

All children will be assigned a unique study ID number. Responses to the allergy questionnaire and oral challenge will be captured on a tablet computer. Data will be entered into RedCap (<http://www.project-redcap.org/>). Additional data points include child’s age in years, child’s sex, race/ethnicity (determined by parent and consistent with NIH guidelines) and visit number.

For children who receive an oral challenge, additional data will include the time of medication administration and time of discharge from the PED. The details of any reaction that occurred and corresponding treatment will also be captured. Final ED disposition will be recorded, and home contact information confirmed for follow-up.

Data Analysis:

Descriptive statistics will be used to summarize baseline patient characteristics, allergy questionnaire, and oral challenge data. The percentage of patients who are eligible for oral challenge will be determined. The percent

of patients/families that refuse an oral challenge or that have providers who are unwilling to conduct an oral challenge in the PED will be documented. The frequency of positive oral challenges will be analyzed and reported using a 95% confidence interval. Descriptive statistics will be used to summarize day 1 and 7 patient characteristics and follow-up questionnaire data. The percentage of patients that are lost to follow-up after an oral challenge will be determined. The frequency of delayed allergic reactions after oral challenge will be analyzed and reported using a 95% confidence interval. SPSS version 22 will be used to perform all analyses. SPSS version 22 will be used to perform all analyses.

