Descriptive characteristics will also be used to summarize the baseline patient characteristics and follow-up questionnaire responses for months 6 and 12 of the children who underwent the oral challenge in Aim 1. We will then conduct a three-level economic cost savings analysis. First, in order to calculate the potential cost savings if amoxicillin is filled for all penicillin allergic de-labelled patients, the median retail price of each non-penicillin antibiotic filled will be compared to the median retail price of amoxicillin. Second, we will calculate the cost avoidance savings assuming that patients who fill any amoxicillin/penicillin prescriptions would have filled cefdinir in its place. Lastly, we will extrapolate the total cost savings potentially generated by the approximately 6,700 patients per year treated in our PED who report penicillin allergy.

Sample Size Justification/Power Analysis:

We have determined that we need 50 patients to complete the oral challenge for the feasibility study to be complete. We will consent for questionnaire-screening approximately 250 children to achieve that number. This number is based off of our previous study; during that study 50 patients were approached per month for survey participation, 80% (40) agreed to participation, and 25% (10) of patients were found have high-risk symptoms of allergy and thus were found to be ineligible. Assuming that 50% of patients with low-risk symptoms will have either provider/family refusal to oral challenge this will leave approximately 15 patients per month to complete an oral challenge. Of the 50 children who complete the oral challenge, we estimate that 40 patients will receive a one-time oral challenge and 10 patients will receive an oral challenge and be sent home with a prescription. This estimation is based off of our previous study where approximately 20% of children who were eligible and willing to be tested were discharged home with a prescription antibiotic. If we are able to reach our enrollment goal prior to approaching 500 patients, we will end the feasibility study.

P. FINANCIAL RELATIONSHIPS

The study is funded with internal funds from the section of Pediatric Emergency Medicine and a grant from the Children's Research Institute which support the costs of accomplishing the oral challenges and other associated project costs.

Q. ADVERTISEMENTS / FLIERS

N/A

R. BIBLIOGRAPHY (*list pertinent literature references*)

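### The follow-up thresholds in Hypotheses 2a and 2b are to be judged by a bare percentage; at Section O's size they work as observed targets, not as evidence that the underlying rate exceeds 95% or 90%

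*Combined protocol and SAP*

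**What the plan says.** Section B, Hypothesis 2a: "Next day contact will be possible for over 95% of children who complete an oral challenge". Hypothesis 2b: "Seven-day follow-up will be completed in at least 90% of children who are discharged on a penicillin or other antibiotic". Both sentences go on to say that the result is to demonstrate an ability, to evaluate symptoms after discharge (2a) or to monitor for delayed reactions (2b).

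Section O, Sample Size Justification: "We have determined that we need 50 patients to complete the oral challenge for the feasibility study to be complete". On the split between children without and with a prescription it says: "we estimate that 40 patients will receive a one-time oral challenge and 10 patients will receive an oral challenge and be sent home". The split is taken from a previous study in which "approximately 20% of children who were eligible and willing to be tested were discharged home with a prescription antibiotic".

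Section O, Data Analysis, attaches 95% confidence intervals to the frequency of positive challenges and of delayed reactions. For contact it says only "The percentage of patients that are lost to follow-up after an oral challenge will be determined". No interval, test or success rule is given for 2a or 2b.

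Section E states another size: "We have determined that we need 100 low-risk patients to complete the oral challenge at each of the three sites". Section D describes a single-site feasibility start, with up to two further sites under discussion.

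**The concern.** 2a and 2b each pair a numeric threshold with the word demonstrate, yet they are the follow-up measures left without an interval. A result of 48/50 or 9/10 meets the threshold as a percentage and could be written up as showing that the rate exceeds it. The data would still be compatible with contact rates well below it.

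This matters for Aim 2 because delayed reactions can be observed only in children who are reached. How well the contact rate is known affects how far the planned interval for delayed reactions can be trusted.

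**Working it through.** **Inputs.** Thresholds 95% and 90% (Section B); 50 completers, about 10 with a prescription, prescription rate about 20% (Section O); 100 completers at each of three sites (Section E).

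**The plan's own figures.** 20% × 50 = 10, which reproduces Section O's estimate. Section C reports 100/100 negative challenges with a 95% CI of 96.4% to 100%. The exact (Clopper-Pearson) two-sided lower limit when all n succeed is 0.025^(1/n), and 0.025^(1/100) = 96.4%. So the documents' own interval agrees with the exact method, and I use that method here. The 50 itself cannot be reproduced from a precision or power formula, because Section O gives no such inputs.

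**2a at n = 50.**
- 50/50: lower limit 0.025^(1/50) = 92.9%; one-sided 0.05^(1/50) = 94.2%. Both are below 95%.
- Equivalently, at a true rate of exactly 95%, P(50/50) = 0.95^50 = 0.077, above both 0.05 and 0.025.
- 49/50: lower limit 89.4%. 48/50: 86.3% to 99.5%.
- Smallest n at which perfect contact clears 95%: the first n with 0.95^n ≤ 0.025 is 72 (two-sided 95%); with 0.95^n ≤ 0.05 it is 59 (one-sided).

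**2b at n = 10.**
- 10/10: lower limit 0.025^(1/10) = 69.2%; one-sided 74.1%. At a true 90%, P(10/10) = 0.9^10 = 0.349.
- 9/10: 55.5% to 99.7%.
- Smallest n at which perfect follow-up clears 90%: 36 two-sided, 29 one-sided.

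**Read as an observed target.** With 50 children, over 95% means 48 or more. Binomial tails: P(X ≥ 48) = 0.54 at a true 95% and 0.11 at a true 90%. With 10 children, at least 90% means 9 or 10: P(X ≥ 9) = 0.74 at a true 90% and 0.38 at a true 80%.

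**Section E's size.** The 2b denominators apply Section O's 20% to Section E's numbers, which is an assumption: 20% × 100 = 20 and 20% × 300 = 60.

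| Hypothesis | n | Result | Exact two-sided 95% lower limit |
|---|---|---|---|
| 2a, one site | 100 | 100/100 | 96.4% |
| 2a, one site | 100 | 99/100 | 94.6% |
| 2a, pooled | 300 | 293/300 (smallest that clears 95%) | 95.3% |
| 2b, one site | 20 | 20/20 | 83.2% |
| 2b, pooled | 60 | 59/60 (smallest that clears 90%) | 91.1% |

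**The case against.** The strongest reply is that this is a feasibility study whose follow-up analysis is descriptive. The plan nowhere says that a confidence limit must exceed 95%. Read as an observed proportion, 2a is met by 48/50, and what is to be demonstrated is an ability to follow children, not a population rate. That stands. A reader might infer from the arithmetic that no result in 50 children could support 2a. The documents do not bear that out, for three reasons:

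- The confidence-limit criterion would be brought in from outside.
- The statement depends on the interval method. A Wilson interval agrees with the exact one (92.9% for 50/50), but a two-sided Jeffreys interval has a lower limit of 95.1%. Section O names no method.
- Fifty is only one of two stated sizes. Under Section E, 2a can clear 95% even by the exact method, and 2b can clear 90% once the sites are pooled.

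Two further replies have weight. A percentage given with its denominator lets a reader derive the interval, so nothing is strictly hidden. And no stopping or progression rule depends on the thresholds, since Section L stops the study at accrual. These limit the consequence. They do not explain why reactions get an interval and the two measures with numeric thresholds do not.

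**Conclusion.** The point holds as one of reporting and wording. At Section O's size, 2a and 2b can be assessed as observed targets but cannot, by the exact method, show that the underlying rate exceeds the threshold: the best possible lower limits are 92.9% and 69.2%. A reported 48/50 (86.3% to 99.5%) or 9/10 (55.5% to 99.7%) should not be concluded to show a rate above 95% or 90%.

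The conclusion rests on exact two-sided 95% limits and on Section O's size. At one site of 100, 2a needs perfect contact and 2b, at about 20 children, remains out of reach; pooled at 300, both can be shown. The 20 and 60 for 2b assume that the 20% prescription rate carries over.

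The 2b denominator is also unsettled. The Aim 2 procedure in Section D has the day 7 call after a penicillin prescription, whereas Hypothesis 2b and Section F include any other antibiotic. On the narrower wording fewer than 10 children might be called.

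**What to change.** - **Section O, Data Analysis:** report next-day contact and seven-day follow-up each with numerator, denominator and an exact (Clopper-Pearson) 95% interval.
- **Section B:** say that 95% and 90% are targets for the observed proportion, and drop the wording that the result demonstrates more than that. Treat 2b as descriptive if only about 10 children contribute.
- **Sections E and O:** reconcile the two sizes, then state the precision that the confirmed size gives. Do not hard-code a count such as 48 of 50; it only restates what 2a already implies at 50 and would be wrong at another size.
- **Section B, Section D (Aim 2) and Section F:** reconcile which prescriptions lead to the day 7 call, so that 2b has one denominator.

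The cost is a few sentences and two intervals. This point requires no change in enrolment. The downside is a less favourable follow-up claim.

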Objective

Our primary objective is to demonstrate the feasibility of utilizing a novel penicillin allergy questionnaire in the PED to identify a low-risk group of patients who will complete an oral challenge in the PED to test for an IgE-mediated allergic reaction. This project will begin as a single site feasibility study, however including up to 2 other collaborative sites for enrollment has been favorably discussed. We do not anticipate this to be a single IRB scenario and will submit a timely comprehensive amendment if plans become concrete and the initial data here proves reliable.

Our secondary objective is to examine whether health care outcomes and prescription-related costs are comparable between children who are de-labeled as penicillin allergic after an oral challenge compared to a standard of care group who are not challenged in the PED.

Aim 1: Demonstrate that a low-risk group of children with reported penicillin allergy will complete an oral penicillin challenge during a pediatric emergency department visit.

Design/setting:

This will be a prospective study of children (2-16) presenting to the PED at the Children's Hospital of Wisconsin with a child or parent reported allergy to penicillin.

Population:

[figure not shown]
Inclusion Criteria: Children aged 2-16 with a parent/guardian (hereafter termed parent) reported history of allergy to a penicillin antibiotic in which the reported allergic reaction occurred at least twelve months prior to the current PED visit.

Exclusion Criteria: Children will be excluded:

- If they have a history of severe developmental delay or inability to communicate the effects of an allergic reaction (non-verbal). ED care team discretion can be utilized to determine ability to proceed with study with regards to developmental delay.
- History of a severe allergic reaction to skin tests
- Anaphylaxis in the past six weeks
- Current pregnancy
- Child is currently on a beta blocker medication
- Children who present to the PED with a rash
- Children who present with multiple episodes of vomiting on day of presentation
- Children presenting to the ED for asthma exacerbation
- Patients deemed too acutely ill for participation as deemed by the ED patient care team
- Non-English speaking families
- Wards of the state, in foster care or police custody or detention will be excluded.

Study Procedure (Figure 1):

Figure 1: Study Procedures for Full Protocol

¹Red boxes indicate oral-challenge-only study procedures

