
Design/setting and study population:

This study will include all children from Aim 1 who underwent an oral challenge in the PED after being determined to have low-risk symptoms on the allergy questionnaire.

Study Procedure (Figure 1, Aim 2)

- 1) A follow-up phone call will be made to all families whose child received an oral challenge.
- 2) If a family receives a one-time dose of antibiotic but does not receive a prescription for a penicillin antibiotic then they will be called on day 1 by a research team member who will administer a 5-minute allergy questionnaire that will review any possible symptoms of allergic reaction following the ED visit.
- 3) If a family receives a penicillin antibiotic prescription following the oral challenge, then they will be called on days 1 and 7 by a research team member for a 5-minute allergy questionnaire that will review any possible symptoms of allergic reaction following the ED visit.
- 4) The patient's primary medical provider will also be notified of the oral challenge results for both groups of patients via fax within 7 days of the oral challenge date.

Aim 3: Examine health care outcomes and prescription-related costs associated with illness treatment plans in children who are de-labeled as penicillin allergic after an oral challenge.**Design/setting and study population:**

This study will include children identified as having low-risk symptoms of allergy from Aim 1 who underwent an oral challenge (Group 1), and those who did not undergo an oral challenge in the PED (Group 2).

Study Procedure (Figure 1, Aim 3)

- 1) A follow-up 5-minute phone survey will be completed by research staff to the family. This follow-up will occur after their initial PED visit at 6 and 12 months.
- 2) The follow-up survey will include questions on health care outcomes since the PED visit that include but are not limited to: the number and type of diagnosed infections, number and type of antibiotics given, and allergic reaction history.

E. TOTAL NUMBER OF HUMAN RESEARCH PARTICIPANTS PROPOSED FOR THIS STUDY AT THIS SITE AND GLOBALLY. WHAT ARE THESE NUMBERS BASED ON?

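### Hypothesis 3a predicts similar health care outcomes, but the month 6 and 12 data get only descriptive summaries, so similarity could be concluded from a sample too small to exclude a meaningful excess

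*Combined protocol and SAP*

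**What the plan says.** Section B, Hypothesis 3a, predicts that four kinds of outcome (allergic reactions, number of illnesses, antibiotics prescribed, and emergency, urgent or primary care visits) "will be similar between children de-labeled as penicillin allergic compared to the general population".

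The comparator is not the same elsewhere. The secondary objective in Section D examines whether outcomes and costs are comparable "compared to a standard of care group who are not challenged in the PED". The Aim 3 design sets challenged low-risk children (Group 1) beside low-risk children who were not challenged (Group 2).

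For analysis, Section O says: "Descriptive characteristics will also be used to summarize the baseline patient characteristics and follow-up questionnaire responses for months 6 and 12", and confines this to the children who were challenged in Aim 1. The next sentence turns to costs: "We will then conduct a three-level economic cost savings analysis". Section O does plan intervals elsewhere: "The frequency of positive oral challenges will be analyzed and reported using a 95% confidence interval", and "The frequency of delayed allergic reactions after oral challenge will be analyzed and reported using a 95% confidence interval". The second of these follows the day 1 and day 7 follow-up text.

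On size, Section O says: "We have determined that we need 50 patients to complete the oral challenge for the feasibility study to be complete". Section E asks for 100 completers at each of three sites.

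**The concern.** A prediction of similarity needs a rule by which it could fail. Hypotheses 2a and 2b have one (over 95% and at least 90% follow-up), and 3b is worded as a significant reduction. Hypothesis 3a has no margin, and its data get no interval. A summary of about 50 children can look unremarkable while remaining compatible with a substantial excess.

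At stake is a reassuring statement about the year after de-labeling, including later allergic reactions. A reader of the results could not tell whether the groups were alike or the sample was too small to show otherwise.

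**Working it through.** **1. The plan's own figures.** The accrual arithmetic reproduces: 50 × 0.80 × 0.75 × 0.50 = 15 completers per month. The 50 itself cannot be reproduced, because no error rate, power, effect size, margin or interval width is given. The exact interval quoted in Section C for the earlier study does reproduce: for 100 of 100 negative, the lower limit is 0.025^(1/100) = 96.4%.

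**2. The same exact method applied to Hypothesis 3a.** This step needs only n = 50. For zero events the upper limit is 1 − 0.025^(1/n). For x events it is the 97.5th percentile of Beta(x + 1, n − x).

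| Reactions in 50 | Upper 95% limit |
|---|---|
| 0 | 1 − 0.025^(1/50) = 7.1% |
| 1 | 10.6% |
| 2 | 13.7% |

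If only 40 families were reached, 0 of 40 would allow 8.8%. For orientation, Section C cites reaction rates of under 2% and of 5.8% on re-exposure. Even zero events in 50 would exclude neither.

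**3. How often a real rise in reactions would be non-significant.** The documents give no reference rate for the follow-up year, so 1%, 2% and 5% are assumptions. The benchmark is an exact one-sample binomial test against a fixed rate p0, upper tail at most 0.025, n = 50. The rejection count r is the smallest with P(X ≥ r | p0) ≤ 0.025, and the chance of missing is P(X ≤ r − 1 | true rate).

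| p0 | r | Doubling | Tripling | Four-fold | Five-fold |
|---|---|---|---|---|---|
| 1% | 3 | 92% | 81% | 68% | 54% |
| 2% | 4 | 86% | 65% | 43% | 25% |
| 5% | 7 | 77% | 36% | 10% | 2% |

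Against 50 unchallenged children (a group size the documents do not state), Fisher's exact test misses 2% versus 6% in 97% of studies and 2% versus 10% in 81%.

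**4. Visits.** The documents give neither mean nor variance. Assumed: mean μ = 2 per year, negative binomial with variance μ + 0.5μ². The miss rates below come from simulated two-sided 5% t-tests with n = 50.

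| Excess | Fixed reference | 50 comparators |
|---|---|---|
| +25% | 73% | 80% |
| +50% | 24% | 45% |

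A normal approximation on the log rate ratio gives 62% and 79% for +25%. Across assumed means of 1-4 and dispersions of 0-1, that approximation ranges from 6% to 78% against a fixed reference, and from 53% to 78% if dispersion is 0.5-1.

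As an interval, with a true ratio of 1, the expected upper limit against a fixed reference is exp(1.96 × √((1/2 + 0.5)/50)) = 1.32. Against 50 comparators it is exp(1.96 × √(2 × (1/2 + 0.5)/50)) = 1.48.

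**5. Section E's size.** 3 × 100 = 300 completers. Zero reactions would then bound the rate at 1.2%. Against a fixed reference, tripling is missed 32% of the time at 1% and 5% at 2%. With the visit assumptions of step 4, +25% is missed about 3% of the time against a fixed reference and 20% against 300 comparators. A doubling of reactions is still missed 75% of the time at 1% and 46% at 2%.

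**The case against.** The strongest reply is that Section O plans no significance test for Hypothesis 3a, so the miss rates describe a test the sponsor never proposed. Hypothesis 3a is also a prediction under a secondary objective of a feasibility study, not a decision rule. This stands in part. The miss rates are a benchmark for what 50 children can show, not a forecast of what will be reported. The limits in step 2 do not depend on any test, and leaving *similar* to judgment is no stronger a safeguard than a test.

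A reader might infer that similarity would be the usual finding even if de-labeled children had several times the reactions or 50% more visits. The documents do not support that. Against a fixed reference, the closest match to the general population named in Hypothesis 3a, +50% visits, 2% versus 10% reactions and a tripling from 5% would usually be detected. High miss rates for the largest reaction excesses mostly need a small parallel group, and no size is stated for Group 2. The 50% refusal assumption does not say how many unchallenged families would take follow-up calls.

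Safety is also watched elsewhere: intervals for challenge and delayed reactions, monthly review of the 6 and 12 month results, and review at every 10 challenged children. These reduce the stakes, but they do not supply an interval or a comparison for Hypothesis 3a.

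**Conclusion.** The point holds in a limited form and is a cheap improvement. As written, *similar* has no criterion, and the outcomes behind it have no measure of precision. With 50 completers, a two- to three-fold rise from a 1-2% reaction rate, or 25% more visits with overdispersed counts, could often not be excluded.

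The exact limits rest only on n = 50 with complete follow-up. The miss rates rest on assumed reference rates, visit means and dispersion, and on a two-sided 5% test. With 300 completers most of the quantified shortfall goes, though a doubling of a rare reaction rate would remain hard to exclude and the missing criterion would be unchanged. The feasibility aim is not affected.

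**What to change.** In Section O, report each Hypothesis 3a outcome in challenged children with a 95% confidence interval: exact for the proportion with an allergic reaction, and a rate with its interval for illnesses, antibiotics and visits. Reword Hypothesis 3a to say that these outcomes *will be estimated and described with 95% confidence intervals*, and drop the prediction of similarity.

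If the sponsor keeps *similar*, three things are needed:

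- Settle one comparator, since Section B names the general population while the secondary objective and the Aim 3 design name unchallenged children.
- Report the difference in proportions or the rate ratio with its 95% interval.
- Conclude similarity only if that interval lies inside a margin fixed before the month 6 and 12 data are analysed, and otherwise report the outcome as inconclusive.

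The first option costs wording and a few intervals, with no extra patients. It should be confirmed that the survey asks about visits, because the Aim 3 list of questions, which is open-ended, does not name them. The second option also needs comparator data: no general-population source is described, and Section O does not analyse Group 2. Its downside is that at 50 children most outcomes would probably be reported as inconclusive.
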